#### Serious Adverse Event

An SAE is any untoward medical occurrence that at any dose:

- Results in death

- Is life-threatening (an event which places the patient at immediate risk of death from the event as it occurred. It does not include an event that had it occurred in a more severe form might have caused death)
- Requires inpatient hospitalization or prolongation of existing hospitalization
- Results in persistent or significant disability or incapacity
- Is a congenital anomaly or birth defect
- Is an important medical event that may not be immediately life-threatening or result in death or hospitalization but may jeopardize the patient and may require intervention to prevent one of the other outcomes listed in the definition above (eg, events include allergic bronchospasm requiring intensive treatment in an emergency room or at home, blood dyscrasias, convulsions, or the development of drug dependency or abuse).

## Adverse Events of Clinical Interest

The following are considered to be AEs of clinical interest:

- ALT or AST  $>3 \times \text{ULN}$
- Severe or serious ISRs; ISRs that are associated with a recall phenomenon (reaction at the site of a prior injection with subsequent injections), or those that lead to temporary dose interruption or permanent discontinuation of zilebesiran.

An ISR is defined as a local reaction at or near the site of injection. “At or near” the injection site includes reactions at the injection site, adjacent to the injection site, or a reaction which may shift slightly away from the injection site due to gravity (eg, as may occur with swelling or hematoma). A systemic reaction which includes the injection site, eg, generalized urticaria, other distinct entities or conditions like lymphadenopathy that may be near the injection site is not considered an ISR.

For information on recording and reporting of AEs of clinical interest, see Section 6.5.6.2 and Section 6.5.6.3, respectively.

## Adverse Event Severity

Adverse events are to be graded according to the categories detailed below:

Mild:	Mild; asymptomatic or mild symptoms; clinical or diagnostic observations only; intervention not indicated.
Moderate:	Moderate; minimal, local or noninvasive intervention indicated; limiting age appropriate instrumental activities of daily living (eg, preparing meals, shopping for groceries or clothes, using the telephone, managing money).
Severe:	Severe or medically significant but not immediately life-threatening; hospitalization or prolongation of hospitalization indicated; disabling; limiting self-care activities of daily living (ie, bathing, dressing and undressing, feeding self, using the toilet, taking medications, and not bedridden); OR life-threatening consequences; urgent intervention indicated; OR death related to an adverse event.

Changes in severity should be documented in the medical record to allow assessment of the duration of the event at each level of severity. Adverse events characterized as intermittent require documentation of the start and stop of each incidence. When changes in the severity of an AE occur more frequently than once a day, the maximum severity for the experience that day should be noted. If the severity category changes over a number of days, then those changes should be recorded separately (with distinct onset dates).

Adverse event severity and seriousness are assessed independently. ‘Severity’ characterizes the intensity of an AE. ‘Serious’ is a regulatory definition and serves as a guide to the Sponsor for defining regulatory reporting obligations (see definition for SAE).

### **Relationship of the Adverse Event to Study Treatment**

The relationship of each AE to study drug should be evaluated by the Investigator by a “yes” or “no” response to the question: “Is there a reasonable possibility that the event may have been caused by the study drug?” A “yes” response indicates that the event is considered as related to the study drug.

The relationship of each AE to the protocol-specified background antihypertensive medication should also be assessed by the Investigator.

#### **6.5.6.2. Eliciting and Recording Adverse Events**

##### **Eliciting Adverse Events**

The patient should be asked about medically relevant changes in the patient’s health since the last visit. The patient should also be asked if the patient has been hospitalized, had any accidents, used any new medications, or changed concomitant medication routines (both prescription and over-the-counter). In addition to patient observations, AEs will be documented from any clinically relevant laboratory findings, physical examination findings, ECG changes, or other findings that are relevant to patient safety.

##### **Recording Adverse Events**

The Investigator is responsible for recording non-serious AEs that are observed or reported by the patient after administration of the first dose of study treatment during the Run-in period regardless of their relationship to the study treatment through the end of study. Study treatment is defined as protocol-specified background antihypertensive medication or study drug (zilebesiran or placebo). Non-serious AEs will be followed until the end of study. Events occurring after signing of the ICF and before the Run-in period will be captured as medical history (see Section 6.1), while AEs that occur after study treatment, and baseline events that worsen after study treatment, must be recorded as AEs.

The Investigator is responsible for recording SAEs that are observed or reported by the patient after the time when the informed consent is signed regardless of their relationship to study treatment through the end of study. SAEs will be followed until satisfactory resolution, until baseline level is reached, or until the SAE is considered by the Investigator to be chronic or the patient is stable, as appropriate.

All AEs must be recorded in the source records for the clinical study center and in the eCRF for the patient, whether or not they are considered to be related. Each AE must be described in

detail: onset time and date, description of event, severity, relationship to study treatment, action taken, and outcome (including time and date of resolution, if applicable).

For SAEs, record the event(s) in the eCRF and, as applicable, the SAE form.

For AEs that are considered AEs of clinical interest (Section 6.5.6.1), the supplemental AEs of Clinical Interest eCRF should be completed. Additional clinical and laboratory information may be collected. Refer to eCRF completion guidelines for details on reporting events in the supplemental AEs of Clinical Interest eCRF.

For all ISRs, the Investigator, or delegate, should submit an Injection Site Reaction Signs or Symptoms eCRF, recording additional information regarding each injection site reaction that is entered on the AE eCRF (eg, symptom[s], injection site location, follow-up actions taken).

#### **6.5.6.3. Reporting Adverse Events of Clinical Interest to Sponsor/Designee**

For AEs that are considered AEs of clinical interest (Section 6.5.6.1), the Sponsor or its designee should be notified within 24 hours using the appropriate eCRF.

#### **6.5.6.4. Serious Adverse Events Require Immediate Reporting to Sponsor/Designee**

An assessment of the seriousness of each AE will be made by the Investigator. Any AE and laboratory abnormality that meets the SAE criteria in Section 6.5.6.1 must be reported to the Sponsor or designee immediately and no later than 24 hours from the time that clinical study center staff first learns of the event. All SAEs must be reported regardless of the relationship to study treatment.

The initial report should include at least the following information:

- Patient's study number
- Description and date of onset of the event
- Criterion for serious
- Preliminary assignment of relationship to study treatment, and
- Investigator/site information

To report the SAE, complete the eCRF and, as applicable, the SAE form. Immediately and no later than 24 hours after receipt of follow-up information, the Investigator must update the eCRF and, as applicable, the SAE form.

Appropriate remedial measures should be taken by the Investigator using the Investigator's best medical judgment to treat the SAE. These measures and the patient's response to these measures should be recorded. All SAEs, regardless of relationship to study treatment, will be followed by the Investigator until satisfactory resolution or the Investigator deems the SAE to be chronic or stable. Clinical, laboratory, and diagnostic measures should be employed by the Investigator as needed to adequately determine the etiology of the event.

If the Investigator becomes aware of an SAE with a suspected causal relationship to the study drug that occurs after a patient withdraws from the study, the Investigator shall report the SAE to the Sponsor or designee within 24 hours of first awareness of the event.

If the Investigator becomes aware of an SAE with a suspected causal relationship to the study drug that occurs after the end of the study in a patient, the Investigator shall report the SAE to the Sponsor within 24 hours of first awareness of the event using the paper SAE form.

#### **6.5.6.5. Sponsor Safety Reporting to Regulatory Authorities**

The Sponsor or its representative will report certain study events in an expedited manner to the Food and Drug Administration, the European Medicines Agency's EudraVigilance electronic system according to Clinical Trials Regulation (EU) No 536/2014 (CTR), and to all country Regulatory Authorities where the study is being conducted, according to local applicable regulations.

#### **6.5.6.6. Serious Adverse Event Notification to the Institutional Review Board/Independent Ethics Committee**

Suspected unexpected serious adverse reactions will be reported to the IRB/IEC per their institutional policy by the Investigator or Sponsor (or Sponsor designee) according to country requirements. Copies of each report and documentation of IRB/IEC notification and acknowledgement of receipt will be kept in the Investigator's study file.

#### **6.5.6.7. Pregnancy Reporting**

If a female patient becomes pregnant during the study through safety follow-up (see Section 3.1), the Investigator must report the pregnancy to the Sponsor or designee within 24 hours of being notified of the pregnancy. Details of the pregnancy will be recorded on the pregnancy reporting form. The patient should receive any necessary counseling regarding the risks of continuing the pregnancy, the possible effects on the fetus, and be counseled to not breastfeed for 90 days after the last dose of study drug.

The pregnancy should be followed by the Investigator until completion. At the completion of the pregnancy, the Investigator will document the outcome of the pregnancy. If the outcome of the pregnancy results in a postpartum complication, spontaneous abortion, stillbirth, neonatal death, or congenital anomaly, then the Investigator should follow the procedures for reporting an SAE as outlined in Section 6.5.6.4.

#### **6.5.6.8. Reporting of Overdose and Other Special Situations**

An overdose is defined as any dose of study drug administered to the participant or taken by the participant that is  $>2\times$  the assigned dose during a single administration and/or  $\geq 2$  doses within  $\frac{1}{2}$  the intended dosing interval.

The Sponsor does not recommend specific treatment for an overdose.

In an event of an overdose or other special situations (eg, medication error, abuse, misuse, or CPC associated with an AE), the Investigator should:

- Contact the Medical Monitor and Sponsor within 24 hours using the contact information in the Pharmacy Manual
- Closely monitor the participant for any AE/SAE and laboratory abnormalities
- Document the amount of study drug given

Signs, symptoms, or the clinical sequelae of a suspected overdose of either study intervention or a concomitant medication will be considered AEs/SAEs.

Full details of reporting instructions for overdose and other special situations will be outlined in the Pharmacy Manual.

## 6.6. Biomarkers, DNA Genotyping, and Biospecimen Repository

Alnylam's RNAi therapeutics platform permits the highly specific targeting of investigational therapies based on genetic sequence. It is possible that variations in the target genetic sequence will result in variations in drug effect. More generally, genetic variations may account for the well-described heterogeneous manifestations of disease in patients with hypertension, as well as their responses to treatment.

Where allowed per local regulations, ethics committee (IRB/IEC) approval, and patient consent, samples will be collected as part of this study to permit exploratory investigations and the application of novel approaches to bioanalyses that may further elucidate the outcomes of this study, or potentially advance understanding of the safety, mechanism of action, and/or efficacy of zilebesiran.

Biological specimens will be collected at the intervals indicated in the Schedule of Assessments ([Table 1](#)). These specimens will be analyzed at a central laboratory. Potential exploratory investigations may include DNA, RNA, or biochemical metabolite assessments as they relate to disease progression, efficacy, or safety.

The biospecimen repository will also include residual material from routine samples (safety laboratory samples, PK samples, etc) that are obtained during the study.

These specimens will be securely stored in a central biorepository for up to 10 years following the completion of this clinical study (ie, last patient last visit), or as per local regulations. After 10 years have elapsed, samples will be destroyed.

Details regarding the collection, processing, storage, and shipping of the samples will be provided in the Laboratory Manual.

Exploratory analysis of these biospecimens will be performed by Alnylam Pharmaceuticals or its designees.

When biobanking is permitted by local regulation, study participants will be advised during the informed consent process of these biobanking details and the potential for exploratory investigation of their samples.

## 7. STATISTICS

A Statistical Analysis Plan (SAP) will be finalized before study unblinding for the analysis of the primary endpoints and secondary endpoints measured at Month 3. The plan will detail the implementation of the statistical analyses in accordance with the principal features stated in the protocol.

## 7.1. Determination of Sample Size

Approximately 630 patients will be randomized to receive either zilebesiran or placebo with sample sizes in each of the patient cohorts with protocol-specified background antihypertensive medication as follows:

- Olmesartan cohort: 300 patients
- Amlodipine cohort: 210 patients
- Indapamide cohort: 120 patients

Assuming a standard deviation of 16 mmHg in change from baseline in 24-hour mean SBP assessed by ABPM and 15% dropout rate from baseline to Month 3, with 2-sided significance level of 0.05 for each of the comparisons (zilebesiran versus placebo as add-on to olmesartan; zilebesiran versus placebo as add-on to amlodipine; zilebesiran versus placebo as add-on to indapamide), these sample sizes will provide at least 80% power to detect the following difference between zilebesiran versus placebo:

- 5 mmHg as add-on to olmesartan
- 6 mmHg as add-on to amlodipine
- 8 mmHg as add-on to indapamide

The power is assessed by simulation based on the Mixed Model with Repeated Measurements (MMRM), with change from baseline in 24-hour mean SBP assessed by ABPM at Month 3 as response variable and treatment, time, treatment-by-time as fixed factors and corresponding baseline value as a covariate.

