#### **Patient and Disease Characteristics**

3. Has hypertension as follows:
  - a. Untreated hypertension (not taking antihypertensive medication), or
  - b. Treated hypertension on stable therapy with up to 2 antihypertensive medications.  
Stable therapy is defined as having no change in antihypertensive medication or dose within 30 days prior to screening.

4. Seated office SBP at Run-in Visit 1 as follows:
  - a.  $\geq 155$  mmHg and  $\leq 180$  mmHg for patients with untreated hypertension
  - b.  $\geq 145$  mmHg and  $\leq 180$  mmHg for patients on antihypertensive medications
5. 24-hour mean SBP  $\geq 130$  mmHg and  $\leq 160$  mmHg by ABPM at Run-in Visit 2 after at least 4 weeks of run-in.
6.  $\geq 80\%$  adherence to the protocol-specified background antihypertensive medication during the Run-in period as assessed by pill count performed at Run-in Visit 2.

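### The stated power of at least 80% in each cohort does not follow from the printed inputs, and under the trial's own baseline window it is at best a favourable-case figure

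*Protocol*

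**What the plan says.** Protocol Section 7.1 plans 300, 210 and 120 patients in the olmesartan, amlodipine and indapamide cohorts. It sets out its assumptions: "Assuming a standard deviation of 16 mmHg in change from baseline in 24-hour mean SBP assessed by ABPM", a "15% dropout rate from baseline to Month 3", and testing "with 2-sided significance level of 0.05 for each of the comparisons". From these it concludes that "these sample sizes will provide at least 80% power to detect the following difference between zilebesiran versus placebo", namely 5, 6 and 8 mmHg. It then names the method: "The power is assessed by simulation based on the Mixed Model with Repeated Measurements (MMRM"), with treatment, time, their interaction and the baseline value in the model. It does not print the baseline SD, the baseline-to-Month 3 correlation, the between-visit correlation or the timing of dropout.

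The Synopsis (Statistical Methods) repeats the inputs and the power claim without mentioning a simulation or an MMRM. Section 4.1, criterion 5, requires a 24-hour mean SBP from 130 to 160 mmHg "by ABPM at Run-in Visit 2 after at least 4 weeks of run-in".

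**The concern.** The section prints every input of a standard two-sample power calculation, and that calculation falls nine to ten percentage points short of 80% in all three cohorts. The named method could close the gap. It can do so only through quantities that are not printed, and one of them, the spread of baseline blood pressure, is limited by the trial's own entry window.

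Each cohort carries its own primary test at 0.05, and the key secondary endpoints follow in hierarchical order. If power is overstated, the chance of missing a true effect of the planned size is understated, and a null result in a cohort would be read as stronger evidence of no effect than it is.

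**Working it through.** **Inputs.** From Section 7.1: SD of change 16 mmHg; dropout 15%; two-sided 0.05; N = 300/210/120; differences 5/6/8 mmHg. From Section 3.4: 1:1 allocation, so 150/105/60 per arm, or 127.5/89.25/51 after 15% loss.

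**Step 1: the plan's figure from the printed inputs.** SE = 16 × √(2/n); power = Φ(difference/SE − 1.96); difference detectable at 80% = 2.80 × SE.

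| Cohort | SE, no loss | Power, no loss | SE, 15% loss | Power, 15% loss | Detectable at 80%, 15% loss |
|---|---|---|---|---|---|
| Olmesartan, 5 mmHg | 1.85 | 77.2% | 2.00 | 70.4% | 5.61 mmHg |
| Amlodipine, 6 mmHg | 2.21 | 77.6% | 2.40 | 70.7% | 6.71 mmHg |
| Indapamide, 8 mmHg | 2.92 | 78.2% | 3.17 | 71.4% | 8.88 mmHg |

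The noncentral t gives 70.0/70.3/70.6% with loss. The stated 80% is not reproduced. An unadjusted test would need 379/264/149 randomized patients to reach it.

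**Step 2: what the MMRM has to add.** It can help in two ways, and they combine.
- Baseline adjustment lowers the SD to 16 × √(1 − R²), where R² is the share of the variance of the change explained by baseline.
- Earlier ABPM readings recover part of the dropout loss. In a large-sample two-visit approximation, effective n = n/f with f = (1 − ρ²)/0.85 + ρ²/(1 − d₀). Here ρ is the residual correlation of the early reading with Month 3, and d₀ is the fraction of patients with no post-baseline reading.

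The SD needed for 80% is difference/(2.80 × √(2/effective n)), and the R² needed is 1 − (that SD/16)² (olmesartan/amlodipine/indapamide):
- No recovery (f = 1.176): SD 14.25/14.31/14.42, R² 0.21/0.20/0.19.
- Every dropout has an early reading, ρ = 0.6 (f = 1.113): R² 0.16/0.16/0.14.
- The same with ρ = 0.8 (f = 1.064): R² 0.12/0.12/0.10.
- Limit of full recovery (f = 1, as if nobody dropped out): R² 0.07/0.06/0.04.

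So the realistic requirement is an R² of about 0.10 to 0.21.

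**Step 3: what criterion 5 allows.** A baseline spread evenly over 130-160 mmHg has an SD of 30/√12 = 8.66. The largest SD possible in that window is 15, with half the patients at each end. If the change falls by b mmHg per mmHg of baseline, R² = (b × baseline SD/16)². Assuming a baseline SD of 7-8.66 and b of 0.3-0.7 (neither is in the protocol), R² runs from (0.3 × 7/16)² = 0.017 to (0.7 × 8.66/16)² = 0.144.

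Worked example for olmesartan, SD 8.66, b = 0.5, no recovery: R² = 0.073; residual SD = 16 × √0.927 = 15.40; SE = 15.40 × √(2/127.5) = 1.93; power = Φ(5/1.93 − 1.96) = 73.6%. Other settings (olmesartan/amlodipine/indapamide, %):

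| Dropout recovery | SD 7, b 0.3 | SD 8.66, b 0.5 | SD 8.66, b 0.7 |
|---|---|---|---|
| None | 71.1/71.5/72.1 | 73.6/74.0/74.6 | 76.9/77.2/77.9 |
| Half have an early reading, ρ 0.5 | 72.0/72.3/73.0 | 74.5/74.8/75.5 | 77.8/78.1/78.7 |
| Half have an early reading, ρ 0.8 | 73.4/73.7/74.4 | 75.9/76.2/76.8 | 79.1/79.4/80.0 |
| All have an early reading, ρ 0.8 | 75.4/75.7/76.4 | 77.8/78.1/78.8 | 80.9/81.2/81.8 |

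With up to half of the dropouts recoverable, the range is 71-80%. Only the most generous recovery combined with the steepest slope goes past 80%.

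**Step 4: the textbook route to 80%.** With equal SDs at baseline and Month 3 and correlation r, the residual SD is 16 × √((1 + r)/2). For r = 0.5 this gives 82.2/82.4/83.0%, and for r = 0.6 it gives 79.7/80.0/80.6%. But an SD of change of 16 then implies a baseline SD of 16/√(2(1 − r)), which is 16.0 at r = 0.5 and 17.9 at r = 0.6. Both exceed the maximum of 15. Under equal variances r cannot exceed 1 − 256/(2 × 225) = 0.43, and even r = 0 needs a baseline SD of 11.3, wider than an even spread over the window.

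**The case against.** The protocol does not claim 80% for an unadjusted test of completers. It names an MMRM simulation with baseline as a covariate, and a simulated figure whose correlations are not printed cannot be rerun, which is not the same as being wrong. Baseline adjustment and dropout recovery combine, so a required R² of 0.19-0.21 is the no-recovery case only. The planned analysis model (Section 7.2.5) also includes race and screening eGFR, which would add a little power if they are prognostic. The slopes, correlations and baseline SDs used above are assumptions.

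All of that stands, and it rules out three stronger readings.
- A reader might infer that the true power is 70-71%. That figure belongs to an unadjusted comparison and is a conservative bound for the planned model.
- A reader might infer that 80% is impossible. It is not: it needs an R² of about 0.10-0.21, and the unprinted inputs could in principle supply that.
- A reader might notice that a one-sided 0.05 test with 15% dropout gives 80.2/80.5/81.1%, or that a baseline SD of 16 with r = 0.5 gives about 82%, and infer that one of these was used. Section 7.1 says two-sided and prints no baseline SD, so neither match shows an error.

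The objection does not restore the claim as worded. The text says at least 80%, and the Synopsis presents that as following from an SD of 16 and 15% dropout alone. Nor does reading 16 as a residual SD help. The gain from baseline would then already be spent, and 77-78% would be the ceiling even with full recovery of dropouts.

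**Conclusion.** The concern holds in a limited form. The printed inputs do not give 80% in any cohort: 70-71% unadjusted with 15% dropout, 77-78% with none. With the named model, a 15% loss and a baseline that criterion 5 permits, power is about 71-80%, mostly 72-78%. The chance of missing the planned effect is then about 20-29%, against a stated maximum of 20%.

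This rests on 16 mmHg being the raw SD of change, as the text says; a baseline SD of 7-8.7 mmHg; slopes of 0.3-0.7; and partial recovery of dropouts. A steeper slope, or near-complete recovery with a strong between-visit correlation, would bring 80% within reach. The stated figure is therefore a favourable case presented as a minimum. The endpoint, estimator, significance level and sample size are unaffected.

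**What to change.** Rerun the simulation with a baseline distribution that criterion 5 allows. Use, and print, a stated range for the baseline-to-Month 3 slope or correlation, the between-visit correlation and the timing of dropout. State whether 16 mmHg is a raw or a residual SD, and confirm that the simulated test was two-sided at 0.05.

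Then, in both the Synopsis and Section 7.1, replace the claim of at least 80% with the resulting power for 5, 6 and 8 mmHg, or with the differences detectable at 80% power. Name the simulation in the Synopsis too. Give the unadjusted result as the conservative bound: 70-71% power, or 5.6, 6.7 and 8.9 mmHg at 80%.

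The cost is one rerun and a few sentences, with no change in enrolment. The stated power will probably be less favourable.
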